4.2. Treatment of Subjects

Subjects will receive all four study injections (120 mg/0.3 mL of TV-46046, 60 mg/0.3 mL of 1:1 saline-diluted TV-46046, 0.3 mL of TV-46046 Placebo and 104 mg/0.65 mL of Depo subQ 104) on the same day approximately 1 hour apart. The four injections will be administered subcutaneously in four abdominal quadrants starting with the subject's right upper quadrant (injection A) and progressing in a clockwise manner to the left upper quadrant (injection B), left lower quadrant (injection C), and right lower quadrant (injection D), per the assigned sequence. The study staff administering the injections will be instructed not to apply bandages, and to avoid touching or massaging the injection site. In case of bleeding, a gentle application of the cotton ball for several minutes will be recommended (ie, no application of ice or bandages). Subjects

will remain at the investigational center for at least 1 hour after the last injection. The investigational center will have an epinephrine injection available and easy access to emergency care in the unlikely event of anaphylaxis or anaphylactoid reaction.

Table 2:	Investigational Medicinal Products Used in the Study

IMP name	TV-46046	TV-46046 Placebo	Reference IMP	
Trade name and INN, if applicable, or company assigned number	Medroxyprogesterone acetate	TV-46046 Placebo	Medroxyprogesterone acetate injectable suspension	
Unit dose strength(s)/ Dosage level(s)	120 mg/0.3 mL (diluted TV-46046: 60 mg/0.3 mL)	0.3 mL	104 mg/0.65 mL	
Route of administration	SC injection	SC injection	SC injection with 26G needle	
	(Sol Care Safety syringe 0.5 ml,	(Sol Care Safety syringe 0.5 ml,		
	with fixed needle $23G \times 3/8$ "	with fixed needle 23G x 3/8"		
	[0.6mm x 10mm]	[0.6mm x 10mm]		

 IMP=investigational medicinal product; INN=international proprietary name; NA=not applicable; anh=anhydrous; qs=quantify sufficient; SC=subcutaneous; G=gauge.

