8.7. Analysis of Secondary Endpoints

8.7.1. Injection Site Pain

NRS pain scores for assessments on the day of injection (Day 0) will be summarized by treatment group in frequency tables, separately for pain measured immediately after (ie, as soon as possible but no later than 10 minutes upon removing the needle) injection and at 1 hour after injection. If an appropriate distribution of pain scores can be identified in the blinded review (e.g., continuous, negative binomial or Poisson), then generalized linear models with exchangeable working correlation structure to account for correlated data will be used to compare treatment groups. The primary analysis model will only include effects of treatment, but exploratory analyses will be performed to assess effects of injection order, age, previous experience with injectable contraceptives, and race. If the dispersion of NRS scores is not amenable to parametric regression methods, then rank-order, permutation tests will be used to compare treatment groups (excluding any subjects who did not receive both injections being compared).

Approximately 1 hour after completing their sequence of the four treatments, each subject will also be asked to rank the injections according to overall pain from least [1] to most [4] painful. The ranking of treatments will be summarized in a frequency table, restricted to subjects who received all four injections. Differences in ranking of most painful injection will be assessed using an exact multinomial test for homogeneity across groups.

The proportion of subjects who self-report injection site pain during the follow-up will be compared between the treatment groups using exact, pair-wise McNemar tests

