#### 2. STUDY DESIGN

#### 2.1. General Design

This is a randomized, crossover, single-center, Phase 1 study to evaluate and compare local tolerability following subcutaneous administration of TV-46046, diluted TV-46046, TV-46046 Placebo, and Depo-subQ 104, in 24 healthy female subjects 18 to 55 years of age. After signing the informed consent form, eligible subjects will be enrolled and receive one of each of the four subcutaneous study injections in each abdominal quadrant: 120 mg/0.3 mL of TV-46046, 60 mg/0.3 mL of 1:1 saline diluted TV-46046, 0.3 mL of TV-46046 Placebo and 104 mg/0.65 mL Depo-subQ 104 per the randomly assigned sequence. Injections will be administered in different quadrants of the abdomen, each separated by approximately 1 hour (sufficient time to eliminate carry-over effect of pain at previous injection). Subjects will be randomized to one of 24 different injection sequences (one subject per sequence) to counterbalance potential effects of injection order or abdominal quadrant on study outcomes.

All subjects will be followed for at least 6 months after receiving their injections. Local tolerability will be assessed by evaluating ISRs at least twice on the day of the study injections (Day 0: immediately after [ie, as soon as possible but no later than 10 minutes upon removing the needle] and 1 hour [±5 minutes] after the injection), at Days 1, 3, 7, and 14; at Months 3 and 6; and at other visits, if indicated. Subjects with unresolved ISR(s) at Month 6 will be followed monthly through the resolution of ISR(s) or Month 18, whichever comes first.

Subjects will assess their injection site pain using an 11-point NRS (0 = no pain at all; 10 = worst pain) twice on the day of injection (Day 0: immediately after [ie, as soon as possible but no later than 10 minutes upon removing the needle] and 1 hour [ $\pm 5$  minutes] after the injection). In addition, 1 hour after the fourth (final) injection subjects will provide an overall ranking of administrations from least [1] to most [4] painful. Thereafter, injection site pain will be assessed

Local Tolerability Study - Contraception Statistical Analysis Plan Version 2.0 TV46046-WH-10147 /1191167 by self-reports at all subsequent visits. Adverse events and concomitant medications will be recorded throughout the study. Vital signs and weight will be measured at baseline and study exit.

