## 2.2. Randomization and Blinding

Each eligible subject will be randomized to one of the 24 possible treatment sequences (one subject per sequence). The randomization scheme will result in each drug being injected first, second, third, and fourth on 6 occasions; and each drug being injected in each quadrant of the abdomen on 6 occasions.

The randomization sequence will be developed by an FHI 360 Randomization Statistician not otherwise involved in the study using a validated SAS® program. Details will be documented in a separate Randomization Request Form prior to study initiation.

Allocation assignments will be concealed for the duration of the trial using a centralized randomization application implemented within the OpenClinica data management system, with sequentially-numbered concealed envelopes available at the investigational center as a back-up method of assignment. The next available randomization sequence will be assigned to each subject only after she has been enrolled into the study.

The study will only be partially blinded due to differences in appearance and volume of the treatments. Designated unblinded site study staff will conduct allocation procedures. Records of treatment sequence assignment will be maintained in a secure manner accessible only to authorized unblinded site study staff. All unblinded site staff involved in allocation procedures will conceal the study drug sequence assignment and all records containing allocation sequence from the subject and blinded site staff. All FHI 360 staff (aside from the unblinded clinical monitor) and sponsor staff will be blinded to treatment sequence until at least the first interim analysis, at which time results may be reviewed by treatment to inform decisions whether to stop enrollment or modify the study. Any cases of unscheduled unblinding, whether for safety reasons or inadvertently, will be described in the CSR.

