#### 2.5. Sample Size and Power Considerations

The study size of 24 subjects (N=24) will provide at least 80% power to detect differences in ISR rates of the magnitude (>40%) observed in recent non-comparative studies of TV-46046 and Depo-subQ 104. Although not designed to obtain precise estimates of less frequent ISR rates (eg, injection site discoloration [hypopigmentation]), there is a high (>90%) probability of detecting one or more specific ISR types if the true rate of such events is at least 10%. No randomized subjects will be replaced. However, if more than two subjects fail to receive all four injections or discontinue before Month 6, then additional subjects may be enrolled to help ensure that there are at least 22 who complete the treatment sequence and are evaluable for at least 6 months. The

Local Tolerability Study - Contraception Statistical Analysis Plan Version 2.0 TV46046-WH-10147 /1191167 additional subjects will be assigned new randomization numbers, and will not re-use the randomization numbers from subjects who did not received all 4 injections.

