# 6.3. Injection Site Pain

NRS pain scores for assessments on the day of injection (Day 0) will be summarized by treatment group in frequency tables, separately for pain measured immediately after injection and at 1 hour after injection. If an appropriate distribution of pain scores can be identified in blinded review (e.g., negative binomial or Poisson), then generalized linear models with exchangeable working correlation structure to account for correlated data will be used to compare treatment groups. The analysis model will only include effects of treatment, but exploratory analyses will be performed to assess effects of injection order, age, and race. If the dispersion of NRS scores is not amenable to parametric regression methods, then rank-order, permutation tests will be used to compare treatment groups (excluding any subjects who did not receive both injections being compared).

Approximately 1 hour after completing their sequence of the four treatments, each subject will also be asked to rank the injections according to overall pain from least [1] to most [4] painful. The ranking of treatment group pain will be summarized in bar charts and frequency tables, restricted to subjects who received all four injections. Differences in ranking of most painful injection will be assessed using an exact multinomial test for homogeneity across groups. If a subject cannot rank all of her injections from least to most painful, or cannot uniquely identify which injection was most painful, then her responses will be appropriately weighted across groups (e.g., if a subject ranks all 4 treatments as equally most painful, then that subject will contribute a score of 0.25 to each group when assessing distribution of most painful injection).

The proportion of subjects with unsolicited reports of injection site pain at one or more follow-up visits after Day 0 will be tabulated and compared between treatment groups using exact, pairwise McNemar tests.

Listings of pain score data will include subjects who received partial injections.

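### Optional improvement: put injection position, the factor the 24 sequences were built to balance, into the main NRS pain model instead of leaving it to exploratory analysis

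*SAP*

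**What the plan says.** SAP 6.3 plans that, if a suitable distribution is found in blinded review, "generalized linear models with exchangeable working correlation structure to account for correlated data will be used to compare treatment groups". It then adds: "The analysis model will only include effects of treatment, but exploratory analyses will be performed to assess effects of injection order, age, and race". Protocol 8.7.1 agrees: "The primary analysis model will only include effects of treatment, but exploratory analyses will be performed to assess effects of injection order". The fallback is a rank-order permutation test. SAP 6.3 names no variance estimator for pain.

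Protocol 4.2 fixes the route for every woman: right upper, left upper, left lower, then right lower quadrant. SAP 2.1 says the 24 sequences are there to "counterbalance potential effects of injection order or abdominal quadrant on study outcomes". SAP 2.2 says the scheme results in each drug being given in each order position six times and "each drug being injected in each quadrant of the abdomen on 6 occasions".

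SAP 3 and 8.1 record that three of the planned 24 women had a partial injection, that three more women were to be enrolled, and that women with a partial injection are left out of the pain-score analysis. On sequences for added women, SAP 2.5 says only that the "additional subjects will be assigned new randomization numbers, and will not re-use the randomization numbers from subjects" who missed injections. On the randomization scheme, SAP 2.2 adds: "Details will be documented in a separate Randomization Request Form prior to study initiation". That form is not among the documents.

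**The concern.** The route is fixed, so the first injection is always in the right upper quadrant, the second always in the left upper, and so on. Order and quadrant cannot be separated and act as one four-level factor. The allocation scheme was built around that factor, yet the main pain model omits it.

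What is at stake is precision. When position is balanced but not modelled, its variance is counted as noise in each treatment contrast. The estimated standard error is then too large for the estimate's real variability, and power falls. This happens even with exactly six per cell.

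A smaller matter is that the six-per-cell count was a property of the original 24 women. With three excluded from the pain set and three added, the visible text no longer assures it.

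**Working it through.** **Reproducing the plan's figure.** Listing all 4! = 24 orders and counting drug by position gives exactly 6 in all 16 cells, as SAP 2.2 states.

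**After the change in women.**
- All treated women: 24 + 3 = 27, if all were treated. 27 / 4 = 6.75 per cell, so six per cell cannot hold in that set.
- Pain set: 24 - 3 + 3 = 24, if no added woman had a partial injection. Six per cell holds only if the added sequences offset the removed ones.
- If removals and additions are random (an assumption), enumerating 2,024 removals by 13,824 additions keeps six per cell in 0.07% of cases. Some cell is off by 2 or more in 82%.
- The resulting chance bias in a pairwise contrast has mean 0. Its SD is 0.09 points at a 1.5-point position span and 0.18 at 3 points, against a standard error of about 0.43.

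**Why balance does not restore precision.** Inputs, all assumed because the documents give none: 24 women, within-woman SD 1.5, position means rising linearly by a total span s.
- A paired treatment difference has variance 2 x 1.5² = 4.5 without position effects. The true SE under balance is √(4.5/24) = 0.433.
- Of the six pairs of positions, three differ by s/3, two by 2s/3 and one by s. The mean squared gap is (3/9 + 8/9 + 1)s²/6 = 0.370s².
- The treatment-only model adds this to the error. At s = 1.5 the SE is √((4.5 + 0.833)/24) = 0.471, a ratio of 1.09. At s = 3 it is √((4.5 + 3.333)/24) = 0.571, a ratio of 1.32. At s = 0.75 the ratio is 1.02.

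**Simulation, Gaussian GEE.** Exchangeable working correlation, between-woman SD 1.5, true difference 1.2 points, 21 original plus 3 random sequences, 10,000 runs per case. The corrected SE is Mancl-DeRouen with t on 23 df.

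| Position span (NRS points) | 0 | 0.75 | 1.5 | 2.25 | 3 |
|---|---|---|---|---|---|
| Treatment-only, uncorrected robust SE: type I (%) | 7.0 | 6.4 | 5.3 | 3.7 | 2.5 |
| Same: power | 0.80 | 0.79 | 0.74 | 0.68 | 0.59 |
| Treatment-only, corrected SE: type I (%) | 4.8 | 4.2 | 3.4 | 2.2 | 1.4 |
| Same: power | 0.74 | 0.73 | 0.67 | 0.60 | 0.50 |
| Position added, corrected SE: type I (%) | 4.3 | 4.2 | 4.2 | 4.0 | 3.9 |
| Same: power | 0.72 | 0.73 | 0.72 | 0.73 | 0.72 |

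Position with an uncorrected robust SE gives type I error of 6.9 to 7.7%, so the term should not be added without attention to the variance estimator.

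**Does the gain depend on imbalance?** No. With exactly six per cell and a corrected SE, power goes from 0.68 to 0.73 (span 1.5) and from 0.50 to 0.73 (span 3). With a model-based SE it goes from 0.74 to 0.80 and from 0.55 to 0.78.

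**Simulation, counts.** Poisson GEE, overdispersed counts capped at 10, corrected SE, 4,000 runs per case. At last-to-first position ratios of 1, 1.35, 1.8 and 3, adding position moves power from 0.59 to 0.57, 0.57 to 0.55, 0.54 to 0.56, and 0.42 to 0.53.

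**The case against.** Treatment-only is a defensible model, prespecified alike in both documents. SAP 6.3 also commits to examining injection order, so the question is only which result is labelled the main one. That stands, and it is why this is optional.

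The gains of 5 and 22 points compare models with the same corrected SE, which the SAP does not specify. If the plan is read as using an uncorrected robust SE, raw power improves only above a span of about 2 points: 0.80 falls to 0.72 at span 0, and 0.74 to 0.72 at span 1.5. This also stands. Part of the plan's higher power at small spans comes from type I error of 6 to 7%, but at span 1.5 it is near nominal (5.3%) and still not beaten.

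The SAP's own examples are count distributions, where the gain is small. Against treatment-only with an uncorrected SE in the Poisson setting, power goes from 0.65 to 0.55, 0.64 to 0.55, 0.62 to 0.56 and 0.51 to 0.53 at the four ratios, with type I error of 7.2, 6.6, 6.4 and 4.9% for treatment-only. Only at the threefold ratio is there a gain, of about 2 points.

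A reader might infer that the added and excluded women have unbalanced the pain comparison and biased it. The documents do not show this. The added women's sequences are not given, the Randomization Request Form may contain a rule for them, and chance bias would average zero and be modest beside the SE. Nor do the documents establish a position effect, which SAP 2.1 calls only potential, or any carry-over.

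**Conclusion.** A cheap, optional improvement on a secondary endpoint. The treatment-only test is not invalid, and the two documents do not conflict.

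What holds is narrower: the main pain model omits the one within-woman factor the design was built to balance, and this costs power if position matters. With SE handling held equal, the Gaussian gain is about 5 points at a 1.5-point span and 22 at 3 points. It is nil at 0.75, with a cost of 1 to 2 points when position has no effect. For counts the change is about -2 to +2 points, rising to +11 only at a threefold ratio.

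The main benefit is stability: with position and a suitable SE, Gaussian type I error stays near 4% and power near 0.72 whatever the position effect. All of this rests on assumed position spans, SDs and treatment effects. The comparison with the plan as written also assumes an uncorrected robust SE for pain.

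**What to change.** In SAP 6.3, before statisticians are unblinded:
- Make treatment plus injection position (four levels, labelled as order/quadrant) the main NRS pain model.
- Name a variance estimator that holds type I error at 24 clusters: a small-sample-corrected robust SE such as Mancl-DeRouen with t on clusters minus 1 df, or a model-based SE if the variance model is adequate.
- Keep the treatment-only model, with the same SE method, as a sensitivity analysis.
- Report the achieved drug-by-position counts for the pain set, and cite the rule used for the added women's sequences if the Randomization Request Form holds one.

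The cost is one model term already in the data, one SE option, one small table and a few lines of SAP text. Three degrees of freedom are spent. About 1 to 2 points of power are lost if position has no effect, and raw power is lower than with an uncorrected robust SE when the position effect is small. The SAP Introduction lets the SAP prevail over the protocol, with the difference explained in the CSR.

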8. STATISTICS

This section describes statistical analyses of primary and secondary objectives as foreseen at the time the protocol was written. Further details will be described in a separate statistical analysis plan which will be approved prior to unblinding of study statisticians. Any additional analyses or changes to planned analyses will be fully disclosed in the clinical study report. All statistical analyses will be performed using SAS[®] software Version 9.4 or later. All tests and comparisons between treatment groups will be conducted at the two-sided 0.05 significance level, with no adjustment for multiple comparisons.

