## **1.2.** Secondary Study Objectives and Endpoints

#### **1.2.1.** Secondary Objectives

The secondary objectives of the study are the following:

- To evaluate and compare injection site pain associated with subcutaneous administration of 120 mg/0.3 mL of TV-46046, 60 mg/0.3 mL of 1:1 saline-diluted TV-46046, 0.3 mL of TV-46046 Placebo, and 104 mg/0.65 mL of Depo-subQ 104
- To evaluate the overall safety of subcutaneous, same-day administration of 120 mg/0.3 mL of TV-46046, 60 mg/0.3 mL of 1:1 saline diluted TV-46046, 0.3 mL of TV-46046 Placebo, and 104 mg/0.65 mL of Depo-subQ 104

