#### **1.2.2.** Secondary Endpoints

#### 1.2.2.1. Injection Site Pain

- Injection site pain for each injection assessed by:
  - Numerical Rating Scale (NRS) score twice on the day of injection (Day 0: immediately [ie, as soon as possible but no later than 10 minutes upon removing the needle] after and 1 hour [±5 minutes] after the injection)
  - Self-reports using the NRS on Days 1, 3, 7 and 14, at Months 3 and 6, and at additional visits, if indicated
- Subjects' perception of injection site pain as assessed by an overall ranking of the 4 study injections from least [1] to most [4] painful on the day of injection (Day 0)

Statistical Analysis Plan Version 2.0 **1.2.2.2. Overall Safety** 

- Occurrence of adverse events (AEs)
- Use of concomitant medications (CMs)

Change in vital signs and weight

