# 4. GENERAL ISSUES FOR DATA ANALYSIS

#### 4.1. General

Descriptive statistics for continuous variables will include the number of observed values, the mean, standard deviation (SD), median, minimum, and maximum values. For categorical variables, the number and percentage of subjects with a specific level of the variable will be presented.

All reported p-values will be assessed for statistical significance at the two-sided 0.05 level, and all confidence intervals (CIs) will be computed at the two-sided 95% coverage level.

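### The pain-ranking endpoint is a full 1–4 ranking, but its only test uses the most-painful choice: a valid test that loses power and compares no pair of products on the ranking

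*SAP*

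**What the plan says.** SAP 1.2.2.1, like Protocol 2.2.2.1, lists the women's perception of pain as a secondary endpoint in its own right, "assessed by an overall ranking of the 4 study injections from least [1] to most [4] painful". The objective behind it is comparative: "To evaluate and compare injection site pain associated with subcutaneous administration of 120 mg/0.3 mL of TV-46046" and the three other injections (SAP 1.2.1).

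SAP 6.3 then does two things with the ranking:

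- The full ranking is descriptive: "The ranking of treatment group pain will be summarized in bar charts and frequency tables, restricted to subjects who received all four injections".
- The single test concerns the top rank: "Differences in ranking of most painful injection will be assessed using an exact multinomial test for homogeneity across groups". Protocol 8.7.1 plans the same test.

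The tie rule serves only that test. A woman who calls all four equally worst is split, so "that subject will contribute a score of 0.25 to each group when assessing distribution of most painful injection".

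The other pain measures in SAP 6.3 do get treatment comparisons. Day 0 NRS scores go into generalized linear models, or rank-order permutation tests if no distribution fits. Pain reported after Day 0 gets exact pairwise McNemar tests.

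On error control, SAP 4.1 says "All reported p-values will be assessed for statistical significance at the two-sided 0.05 level", and Protocol 8 says comparisons are made "with no adjustment for multiple comparisons".

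**The concern.** The endpoint and its test do not match. The data are four ranks per woman, but the test keeps only the identity of her rank 4. It asks whether the four products are named worst equally often. Products that differ mainly lower down, for example a vehicle that hurts less than three similar MPA injections, leave only a weak trace there.

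The test is also omnibus. A significant result would not say whether TV-46046 120 mg was ranked above or below Depo-subQ 104, although Protocol 1.4.1 names those two products for direct comparison of local tolerability. Elsewhere the plan does go to pairs: all six for ISRs (SAP 6.2) and pairwise McNemar tests for follow-up pain (SAP 6.3). The ranking is the exception.

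At stake is a secondary result. A real ordering could give a non-significant test that is then read as no difference in ranking.

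**Working it through.** **The plan's own figures.** No power or effect size is stated for the ranking. The stated chance of seeing an event with a true rate of 10% in 24 women reproduces: 1 − 0.9^24 = 0.920, above 90%. The 80% power statement in SAP 2.5 is about ISR rates and does not bear on the ranking.

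**Inputs.** n = 24. SAP 8.1 adds 3 women because 3 of the planned 24 had a partial injection, so 24 + 3 − 3 = 24 if those three are left out of the ranking. Two-sided level 0.05 (SAP 4.1). *Assumption:* each woman's pain is normal with independent within-woman errors of SD 1, and products differ by the mean shifts shown below.

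**Tests compared.**
- *Planned:* exact multinomial on the rank-4 counts, null probability 1/4 each. All C(27,3) = 2,925 outcomes were enumerated, with the p-value by probability ordering. Attained size is 4.74%.
- *Alternative:* Friedman on the full ranks, F = 12/(n·4·5)·ΣRj² − 3n·5, where Rj is the rank sum of product j. The critical value of 7.8 comes from the simulated null.

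Relative loss = 1 − power(planned)/power(Friedman). Simulations used 20,000 trials per pattern.

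| Mean shifts (SD) | Planned | Friedman | Relative loss |
|---|---|---|---|
| 0, 0, 0, 0 (null) | 0.048 | 0.048 | – |
| 0.75, 0, 0, 0 (one worst) | 0.459 | 0.603 | 24% |
| 1, 0, 0, 0 (one worst) | 0.743 | 0.870 | 15% |
| 1, 0.67, 0.33, 0 (graded) | 0.494 | 0.744 | 34% |
| 0.75, 0.75, 0, 0 (two v two) | 0.498 | 0.750 | 34% |
| 0.8, 0.8, 0.4, 0 | 0.351 | 0.626 | 44% |
| 0, 0, 0, −0.75 (one least) | 0.285 | 0.601 | 53% |
| 0, 0, 0, −1 (one least) | 0.446 | 0.865 | 48% |

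The SAP does not say how outcomes are ordered for the exact p-value. With chi-square ordering, the one-worst 1 SD row becomes 0.789 (9% loss) and the one-least 1 SD row 0.363 (58% loss). With 21 women the one-least 1 SD row is 0.376 versus 0.806.

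**Why the last row is so low.** If one product is 1 SD less painful, the chance that it is ranked worst is ∫φ(z+1)Φ(z)³dz ≈ 0.07, and the other three have (1 − 0.07)/3 = 0.31 each, against 0.25 under the null. The signal sits in one sparse cell: about 24 × 0.07 = 1.7 women against 6 expected.

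**A larger effect taken from the documents.** Protocol Table 3 gives injection pain in 8/12 women on TV-46046 and 3/18 on Depo-subQ 104. On a probit scale, Φ⁻¹(0.667) − Φ⁻¹(0.167) = 0.43 + 0.97 = 1.40 SD. Treating that as a within-woman shift is a further assumption, because the data are non-comparative. Order: TV-46046 120 mg, TV-46046 60 mg, Placebo, Depo-subQ 104.

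| Mean shifts (SD) | Planned | Friedman | Relative loss |
|---|---|---|---|
| 1.4, 0, 0, 0 | 0.967 | 0.993 | 3% |
| 1.4, 0.7, 0, 0 | 0.915 | 0.988 | 7% |
| 1.4, 1.4, 0, 0 | 0.968 | 1.000 | 3% |
| 1.4, 0.7, 0.7, 0 | 0.751 | 0.946 | 21% |
| 1.4, 1.4, 1.4, 0 | 0.697 | 0.992 | 30% |

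**A pairwise comparison from the same ranks.** For two products 1 SD apart, the chance that the more painful one is ranked higher is Φ(1/√2) = 0.760. The exact two-sided sign test with n = 24 rejects at 18 or more, or 6 or fewer (p = 0.023 at 6, 0.064 at 7). Its power is P(Bin(24, 0.760) ≥ 18) = 0.65.

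**The case against.** The planned test is pre-specified, the same in both documents, and holds its level. Which injection hurt most is a legitimate tolerability question, and the full ranking will be visible in the tables and charts. All of that stands: this is a matter of efficiency and fit, not of error or bias.

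A reader might infer that the plan never compares pain between products, or that the comparison the trial was built for goes untested. The documents do not support either reading. The primary endpoint is ISRs excluding pain (SAP 1.1.2), and SAP 6.3 compares Day 0 NRS scores and follow-up pain by product. The NRS analysis can detect a less painful Placebo and can contrast TV-46046 with Depo-subQ 104. The gap is confined to the ranking.

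A reader might also take half the power as the general loss. It is not. The trial was prompted by the possibility that TV-46046 is more irritating (Protocol 1.1, 1.4.1). If one product is clearly worst, the loss is small to moderate, and at the effect suggested by Table 3 it ranges from 3% to 30%.

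Finally, the pairwise sign tests add unadjusted comparisons, and the lead one has only moderate power. That is a real cost, though without them the ranking answers no question about any pair.

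**Conclusion.** The mismatch is real and limited. The endpoint is the full ranking, its only test uses the top choice, ranks 1 to 3 are described without inference, and no pair of products is compared on the ranking.

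The planned test is valid. Friedman had the higher power in every non-null pattern tried. The relative loss is about 3–25% with one clear worst product, about a third in graded or two-versus-two patterns of 0.75–1 SD, and about half when one product is 1 SD less painful than the rest. The sizes rest on latent-normal pain, independent within-woman errors, no ties and n = 24. The effect sizes are assumptions, since the documents give none for the ranking.

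This is a cheap improvement to one secondary endpoint. It changes nothing in the ISR analysis or in the other pain comparisons.

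**What to change.** In SAP 6.3:

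1. Make the main test of the ranking a Friedman test on the full within-woman ranks, with a permutation p-value and midranks for ties. Midranks also avoid the fractional counts that the present tie rule would feed into an exact multinomial test.
2. Follow it with exact pairwise sign tests of whether one product was ranked more painful than the other, naming TV-46046 120 mg versus Depo-subQ 104 first.
3. Keep the most-painful table and bar chart as description, or keep the multinomial test as supportive.
4. State whether women with a partial injection are in the ranking analysis. SAP 3 and 8.1 exclude them from the pain score analysis without saying whether that covers the ranking.

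Cost: SAP wording and a standard procedure on data already collected. SAP 2.6.2 allows amendments before database lock. The change should be made before the statisticians are unblinded, or the analysis labelled exploratory. The difference from Protocol 8.7.1 would be explained in the study report, as the SAP introduction provides. The downside is a few more unadjusted secondary comparisons, with about 65% power for a pair 1 SD apart.
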